3.4 Data sharing (if applicable)

Data sharing will be prepared using the CTU Bern Anonymization SOP. Data will be shared on the portal BORIS of the University Bern or equivalent portal. Data can be shared after formal requests with a study proposal are evaluated by the Sponsor.

CTU Bern	Swiss APERO SAP	Version: 2.0	
	Template: CS_STA_TEM-11	Valid from: 17.08.2021	

4. Statistical principles

4.1 Confidence intervals and *P* values

Primary and secondary end points will be analysed on an intention-to-treat basis. Additional analyses will be also carried out in the per-protocol and as-treated populations. Categorical outcome measures will be compared using a χ^2 test or Fisher exact test as required. Continuous variables will be compared using a 2-sided unpaired t test or a Mann-Whitney test, as appropriate. Estimation of the cumulative incidence of safety and efficacy end-points will be performed using the Kaplan-Meier method in case of time-to-event endpoints, and event rates will be compared by the log rank test. The estimated relative risk (RR) is the ratio of the risk probabilities, and a confidence interval will be constructed based on a logarithmic transformation.

The primary endpoint LAA patency or adjudicated cross-over including failed cross-over to other device at 45 days will be analyzed using risk ratios and risk differences.

All statistical tests will be performed using a 5% significance level.

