2.3 Sample size

Considering an incidence of the primary composite end-point in the range of 50% in the Watchman/FLX group, which is a conservative estimate based on previous reports, we estimate that 200 patients will provide greater than 80% power to prove superiority of Amulet as compared to Watchman/FLX assuming a 40% risk reduction (i.e. corresponding to an event rate in the range of 30%) and a significance level of 5% (alpha).

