5.7 Primary and secondary outcomes at 45 days of Follow-up

A Table of the primary and secondary outcomes at 45-day visit will be produced, randomized to Amulet vs randomized to Watchman

Table 4. Primary and secondary outcomes at 45 days

	Watchman/FLX	Amulet	Amulet vs Watchman Mean difference (95% CI)	p-value
	N = xx	N = xx		
Patent Appendage or justified cross-over to non-randomized device	n = xx, xx (%)	n = xx, xx (%)	x.x% (x.x%; x.x%)	x.XXX
Patent Appendage*	n = xx, xx (%)	n = xx, xx (%)	x.x% (x.x%; x.x%)	x.XXX
Justified cross-over to non-randomized device¶	n = xx, xx (%)	n = xx, xx (%)	x.x% (x.x%; x.x%)	x.XXX
Death	n = xx, xx (%)	n = xx, xx (%)	x.x% (x.x%; x.x%)	x.XXX
Cardiovascular death	n = xx, xx (%)	n = xx, xx (%)	x.x% (x.x%; x.x%)	x.XXX
Cerebrovascular event	n = xx, xx (%)	n = xx, xx (%)	x.x% (x.x%; x.x%)	x.XXX
Stroke	n = xx, xx (%)	n = xx, xx (%)	x.x% (x.x%; x.x%)	x.XXX
ischaemic stroke	n = xx, xx (%)	n = xx, xx (%)	x.x% (x.x%; x.x%)	x.XXX
haemorrhagic stroke	n = xx, xx (%)	n = xx, xx (%)	x.x% (x.x%; x.x%)	x.XXX
TIA	n = xx, xx (%)	n = xx, xx (%)	x.x% (x.x%; x.x%)	x.XXX
Systemic or pulmonary embolism	n = xx, xx (%)	n = xx, xx (%)	x.x% (x.x%; x.x%)	x.XXX
Systemic embolism	n = xx, xx (%)	n = xx, xx (%)	x.x% (x.x%; x.x%)	x.XXX
Pulmonary embolism	n = xx, xx (%)	n = xx, xx (%)	x.x% (x.x%; x.x%)	x.XXX
Myocardial infarction	n = xx, xx (%)	n = xx, xx (%)	x.x% (x.x%; x.x%)	x.XXX
Device embolization	n = xx, xx (%)	n = xx, xx (%)	x.x% (x.x%; x.x%)	x.XXX
Bleeding	n = xx, xx (%)	n = xx, xx (%)	x.x% (x.x%; x.x%)	x.XXX
BARC 2	n = xx, xx (%)	n = xx, xx (%)	x.x% (x.x%; x.x%)	x.XXX
BARC 3abc	n = xx, xx (%)	n = xx, xx (%)	x.x% (x.x%; x.x%)	x.XXX
BARC 4	n = xx, xx (%)	n = xx, xx (%)	x.x% (x.x%; x.x%)	x.XXX
BARC 5ab	n = xx, xx (%)	n = xx, xx (%)	x.x% (x.x%; x.x%)	x.XXX
BARC 3-5	n = xx, xx (%)	n = xx, xx (%)	x.x% (x.x%; x.x%)	x.XXX
TIMI major or minor	n = xx, xx (%)	n = xx, xx (%)	x.x% (x.x%; x.x%)	x.XXX
TIMI major	n = xx, xx (%)	n = xx, xx (%)	x.x% (x.x%; x.x%)	x.XXX
TIMI minor	n = xx, xx (%)	n = xx, xx (%)	x.x% (x.x%; x.x%)	x.XXX
TIMI minimal	n = xx, xx (%)	n = xx, xx (%)	x.x% (x.x%; x.x%)	x.XXX
GUSTO moderate or severe	n = xx, xx (%)	n = xx, xx (%)	x.x% (x.x%; x.x%)	x.XXX
GUSTO severe	n = xx, xx (%)	n = xx, xx (%)	x.x% (x.x%; x.x%)	x.XXX
GUSTO moderate	n = xx, xx (%)	n = xx, xx (%)	x.x% (x.x%; x.x%)	x.XXX
GUSTO mild	n = xx, xx (%)	n = xx, xx (%)	x.x% (x.x%; x.x%)	x.XXX
Patient on (N)OAC at 45 days visit	n = xx, xx (%)	n = xx, xx (%)	x.x% (x.x%; x.x%)	x.XXX

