Data expressed as n (%), p-value from Fisher's tests

¶ Justified crossover is defined as the switch from the randomized device to the other device based on morphological/anatomical considerations during device implantation as centrally assessed by an independent and multidisciplinary clinical event committee (CEC). This parameter was included in the composite primary outcome together with *LAA Patency.

CCTA: cardiac computer tomography angiography. TTE: Transthoracic Echocardiography.

CTU Bern	Swiss APERO SAP	Version: 2.0	
	Template: CS_STA_TEM-11	Valid from: 17.08.2021	

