6.2 Analysis methods

6.2.1 Primary analysis

The primary outcome analysis will be conducted by measuring the LAA patency at 45 days using the CCTA, combined with adjudicated cross-over including failed cross-over to another non-randomized LAAC device during the index LAAC procedure.

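### The SAP names no deciding test for the primary composite; the Fisher test printed in Table 4 has 79.2% power, just under the stated claim of more than 80%

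*Combined protocol and SAP*

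**What the plan says.** **Tests.** SAP 4.1 states: "Categorical outcome measures will be compared using a χ^2 test or Fisher exact test as required". It does not say when Fisher is required. Protocol 12.4 has the same provision. SAP 4.1 also states: "All statistical tests will be performed using a 5% significance level". Two-sidedness is written only for the t test: "Continuous variables will be compared using a 2-sided unpaired t test or a Mann-Whitney test, as appropriate".

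**Effect measures.** SAP 4.1 says the primary endpoint "will be analyzed using risk ratios and risk differences", without ranking the two. The risk ratio gets a log-scale confidence interval. No method is given for the risk-difference interval.

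**Primary analysis.** SAP 6.2.1 opens: "The primary outcome analysis will be conducted by measuring the LAA patency at 45 days using the CCTA". It goes on to add adjudicated crossover and stops there, with no test, effect measure or success criterion. SAP 4.3 (Estimands) adds only counts and proportions. The hypotheses in protocol 12.1 and SAP 2.4 are not tied to any statistic.

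**Table 4 (SAP 5.7).** The primary row has a column headed "Amulet vs Watchman Mean difference (95% CI)" and a p-value column. The footnote covers the whole table: "Data expressed as n (%), p-value from Fisher's tests". There is no risk-ratio column.

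**Power.** SAP 2.3 and protocol 12.2 assume 50% vs 30%: "we estimate that 200 patients will provide greater than 80% power to prove superiority of Amulet". The protocol synopsis makes clear that these 200 are patients with the primary endpoint assessed, 100 per arm.

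**The concern.** The trial makes one confirmatory claim, superiority of Amulet on the primary composite, and the plan does not name the test that settles it. Two consequences follow.

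First, the sample-size statement and the Table 4 shell appear to rest on different tests. Fisher's exact test is conservative at these sample sizes. If it decides, the trial has less power than stated.

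Second, Table 4 pairs a Fisher p-value with an interval that will usually come from a different method. Near the 5% boundary the two can point in opposite directions in the same row. Without a named decider, a borderline result could be argued either way once it is known. The trial is open-label and supported by a grant from the manufacturer of one of the two devices (protocol 15), so a rule fixed in advance would protect its conclusion.

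**Working it through.** **Inputs**
- Event rates 50% (Watchman/FLX) and 30% (Amulet), 200 patients, 5% level: SAP 2.3.
- 1:1 allocation: SAP 2.2. 100 per arm with the endpoint assessed: protocol synopsis.
- Assumed: a two-sided test, because the documents give no sidedness for the binary comparison.
- Assumed: a Wald interval for the risk difference, because no method is stated.

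**Step 1: the plan's own figure.** The usual formula for the uncorrected chi-square (pooled z) test, with d = 0.20 and mean rate 0.40:

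power = Φ{[d − 1.96·√(2·0.40·0.60/100)] / √(0.50·0.50/100 + 0.30·0.70/100)}
= Φ{[0.20 − 1.96·0.0693] / 0.0678} = Φ(0.947) = 82.8%.

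With 1.645 in place of 1.96 (one-sided 5%) it is 89.8%. A claim of more than 80% therefore reproduces, and two-sided 5% is the closer fit.

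**Step 2: exact rejection probabilities.** Enumerate all 101 × 101 possible tables with 100 per arm. Weight each by the product of its two binomial probabilities, and add the weights of the tables each rule rejects.

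| True rates | Fisher | Chi-square, uncorrected | Wald RD interval excludes 0 | Wald excludes 0 but Fisher p ≥ 0.05 |
|---|---|---|---|---|
| 50% vs 30% | 79.2% | 83.2% | 83.3% | 4.0% |
| 50% vs 35% | 53.0% | 58.7% | 58.8% | 5.7% |
| 50% vs 50% | 4.0% | 5.6% | 5.6% | 1.6% |
| 40% vs 40% | 3.6% | 5.1% | 5.2% | 1.6% |
| 30% vs 30% | 3.5% | 5.1% | 5.3% | 1.8% |

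Over null rates from 30% to 50% in steps of half a point, exact size runs from 3.4% to 4.0% for Fisher and from 5.0% to 5.6% for chi-square. The opposite conflict (Fisher significant, Wald interval including zero) had probability 0.0000 to four decimals in every scenario.

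**Step 3: one borderline table, 50 vs 36 events.**
- Fisher: p = 0.063.
- Chi-square: pooled rate 0.43, z = 0.14/√(2·0.43·0.57/100) = 0.14/0.0700 = 2.00, p = 0.046.
- Wald: −0.14 ± 1.96·√(0.50·0.50/100 + 0.36·0.64/100) = −0.14 ± 1.96·0.0693, or −27.6% to −0.4%. The Newcombe interval also excludes zero.
- Risk ratio: 0.72·exp{±1.96·√(1/50 − 1/100 + 1/36 − 1/100)} = 0.72·exp(±0.327), or 0.52 to 0.998.

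The zone of conflict is narrow. With 50 control events, all four results favour Amulet at 35 Amulet events (Fisher p = 0.045), and none does at 37 (chi-square p = 0.064).

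**Step 4: is Fisher needed for this row?** The planned counts are 50 events and 50 non-events against 30 and 70. The smallest is 30, so the usual sparse-data reason for Fisher is absent.

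**Sensitivity.** The plan gives no loss rate. If 95 per arm were analysable, exact power at 50% vs 30% would be 76.0% for Fisher and 80.6% for chi-square.

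**The case against.** The strongest reply is that the plan does identify a test. SAP 4.1 keeps tests apart from estimates: chi-square or Fisher at 5% for testing, risk ratio and risk difference for description. The Table 4 footnote then fixes the printed p-value as Fisher. On that reading Fisher decides and the interval only describes the effect. An interval and a p-value built by different methods can disagree near the threshold in any trial.

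Much of this stands. A reader might infer that the SAP sets up several rival decision statistics (chi-square, Fisher, a risk-difference interval and a risk-ratio interval), any of which could be claimed as the verdict. The documents do not support that. Nowhere is an interval said to decide superiority, and Table 4 shows one p-value and one interval, with no risk ratio. Freedom to choose afterwards is also limited. The shell is prespecified, a second statistician works on coded arms and the sponsor first sees coded tables (SAP 2.8), outcomes are double-programmed (SAP 6.7), and deviations must be reported (protocol 12.4).

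The reply does not remove the point. The footnote covers a mixed table that includes rare clinical events, and nothing says it governs the superiority claim. SAP 4.1 allows chi-square for the same outcome, and SAP 6.2.1 is silent. If Fisher was intended, the stated power is slightly too high.

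**Conclusion.** The point holds as a gap in wording with a measurable consequence. The only test attached to the primary row has exact power of 79.2% at the planned rates, 4.0 percentage points below the 83.2% of the chi-square test that SAP 4.1 also allows, and just under the claimed level. A Fisher p-value above 0.05 beside a Wald interval excluding zero would occur in about 4% of trials at the planned rates and 1.6% under no difference at 50%. The effect estimate itself is untouched, and most results would read the same by any method.

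This rests on 100 analysable patients per arm, a two-sided test and the Wald interval. The power comparison does not depend on the Wald choice. The conflict hardly does: chi-square and Fisher differ in 83.2% − 79.2% = 4.0% of trials at the planned rates.

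**What to change.** In SAP 6.2.1, name one deciding test for the primary composite: the uncorrected chi-square (score) test at two-sided 5%. Report with it the risk difference, Amulet minus Watchman/FLX, and the 95% interval obtained by inverting that test, so that the p-value and interval in the primary row agree. State that the risk ratio and its log-scale interval are supportive. Limit the Table 4 Fisher footnote to sparse rows, and say what counts as sparse.

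This choice matches the sample-size statement and changes only SAP wording. Its cost is exact size: about 5.0–5.6% for null rates of 30–50%, slightly above nominal, against 3.4–4.0% for Fisher.

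If the sponsor prefers strict control of the level, Fisher is a defensible alternative. It should then be named in SAP 6.2.1 as the decider, and the power restated as about 79%. Either way, the choice should be recorded before results by arm are seen.

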4.2 Analysis populations

The primary endpoint analysis will be performed using the intention to treat principle on the intention-to-treat, full-analysis set population. Sensitivity analyses will be performed on the per-protocol population. Crossover patients will be considered as a primary end-point event in all analyses.

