12.4 Planned Analyses

Datasets to be analysed, analysis populations

The main analysis of the primary endpoint will be conducted on all randomized patients who have completed the 45-day follow-up according to the intention to treat principle, in keeping with the superiority prespecified study hypothesis. Additional analyses of the primary endpoint will be also carried out in the per-protocol and as-treated populations. Similarly, LAA patency and DRT at 45-day and 13-month CCTA and at 45-day TEE **as well as clinical outcomes** will also be analyzed in the per-protocol and as-treated population.

Primary and secondary Analysis

Primary and secondary end points will be analysed on an intention-to-treat basis; as above mentioned some of them will be analysed also in the per-protocol and as-treated populations. Categorical outcome measures will be compared using a χ^2 test or Fisher exact test as required. Continuous variables will be compared using a 2-sided unpaired t test or a Mann-Whitney test, as appropriate. Estimation of the cumulative incidence of safety and efficacy endpoints will be performed using the Kaplan-Meier method, and event rates will be compared by the log rank test. The estimated relative risk (RR) is the ratio of the risk probabilities, and a confidence interval will be constructed based on a logarithmic transformation. Correlations between variables will be analyzed with a Cox regression.

Interim analyses

No statistical interim analyses planned.

Safety analysis

No statistical interim analyses planned.

Deviation(s) from the original statistical plan

Any deviation from the planned analyses will be reported in the final trial report.

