3.3 Data preparation

LAA patency is derived from the average Linear attenuation coefficient within the LAA distal to the device's lobe (artphase_mean2) ≥ 100 HU OR average Linear attenuation coefficient within the LAA distal to the device's lobe $\geq 25\%$ of the average Linear attenuation coefficient within the LAA (artphase_mean2/artphase_mean1 ≥ 0.25), as recorded inside the follow-up 45 days visit of the Consensus estimate (this is the consensus of the three Core laboratory assessments by three different assessors). LAA patency is a marker of leaks in/out of the LA and therefore a marker of potential thrombus material migration from the LAA to blood circulation system.

Cross-overs are captured in the procedure eCRF and Adjudicated by the clinical event adjudication committee, both successful and failed attempts to cross-over.

CTU Bern	Swiss APERO SAP	Version: 2.0	
	Template: CS_STA_TEM-11	Valid from: 17.08.2021	

The primary endpoint is defined as LA patent or adjudicated cross-overs including failed cross-overs.

Table 1: Derivation of LA patency used in the primary outcome.

Outcome	eCRF sheet	Variable	Variable type	Remarks
LAA patency				
patent = 1	CCTA	fu_reader = 6 = Consensus AND (artphase_mean2 ≥ 100 OR artphase_mean2/artphase_mean1 ≥ 0.25)	Categorical Continuous	Consensus assessment of three assessors LAA HU mean distal from device's lobe in arterial phase = artphase_mean2 LA HU mean in arterial phase = artphase_mean1
not patent = 0				artphase_mean2 not missing and not patent as reverse of the above

Clinical events are also adjudicated and these adjudicated events up to 45 days after the LAAC procedure (or randomization date if no procedure was initiated) will be analysed, excluding events occurring before the LAAC procedure (or randomization date if no procedure was initiated) and excluding events occurring on day 46 and later. Adjudicated events beyond 45 days are used for the longer-term follow-up analyses and censored accordingly (e.g. at 1 year, at 5 years).

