4.2.3 Safety population

The safety population is the population with at least one LAAC device implanted, and is analysed according to the LAAC device actually implanted.

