¶leak visible between the disc and the lobe, but only measured if distance between disc and lobe large enough to allow assessment of hue.

CCTA: cardiac computer tomography angiography assessed by Core Laboratory. TEE: Transthoracic Echocardiography assessed by local team.

includes n=x patient randomized to Watchman / FLX, but were implanted a cross-over Amulet device instead.

Supplemental Table 2. Evaluation of Watchman / FLX implantation post-procedure and at 45 days visit

Watchman / FLX implanted (N=xx)
--

Post-procedural TEE assessment

Maximum device diameter TEE — mm (SD)	n = xx, xx.x ± x.x
Maximum device compression* — % (SD)	n = xx, xx.x ± x.x
Minimum device diameter TEE — mm (SD)	n = xx, xx.x ± x.x
Minimum device compression¶ — % (SD)	n = xx, xx.x ± x.x
Lobe's shape	
inverted — no. (%)	x (x.x%)
marshmallow — no. (%)	x (x.x%)
bell — no. (%)	x (x.x%)
hotdog — no. (%)	x (x.x%)
Position of device from LAA ostium	
at the same level — no. (%)	x (x.x%)
distally — no. (%)	x (x.x%)
proximally — no. (%)	x (x.x%)
Position of the device in respect to the left lateral ridge LLR?	
at the same level — no. (%)	x (x.x%)
distally — no. (%)	x (x.x%)
proximally — no. (%)	x (x.x%)
How far is the Watchman device off-axis to the LAA axis — degrees angulation (SD)	n = xx, xx° ± x°

45 days visit CCTA assessment

Minimum device diameter — mm (SD)	n = xx, xx.x ± x.x
Minimum device compression¶ — % (SD)	n = xx, xx.x ± x.x
Maximum device diameter — mm (SD)	n = xx, xx.x ± x.x
Maximum device compression* — % (SD)	n = xx, xx.x ± x.x
Lobe's shape	
inverted — no. (%)	x (x.x%)
marshmallow — no. (%)	x (x.x%)
bell — no. (%)	x (x.x%)
hotdog — no. (%)	x (x.x%)
Position of device from LAA ostium	
at the same level — no. (%)	x (x.x%)

CTU Bern	Swiss APERO SAP	Version: 2.0	
	Template: CS_STA_TEM-11	Valid from: 17.08.2021	

distally — no. (%)	x (x.x%)
proximally — no. (%)	x (x.x%)
Position of the device in respect to the left lateral ridge LLR?	
at the same level — no. (%)	x (x.x%)
distally — no. (%)	x (x.x%)
proximally — no. (%)	x (x.x%)
How far is the device from the left lateral ridge LLR? — mm (SD)	n = xx, xx.x ± x.x
How far is the Watchman device off-axis to the LAA axis — degrees angulation (SD)	n = xx, xx° ± x°

Only successfully implanted LAAC devices evaluated.

*(Manufacturer device diameter - maximum implanted device diameter)*100%

¶(Manufacturer device diameter - minimum implanted device diameter)*100%

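### SAP 4.2 makes every crossover a primary event in all analyses but defines no as-treated set; grouped by implanted device, the allocated device's failure is charged to its replacement

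*Combined protocol and SAP*

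**What the plan says.** Protocol 12.4 commits to more than the intention-to-treat analysis: "Additional analyses of the primary endpoint will be also carried out in the per-protocol and as-treated populations". The synopsis says the same, and SAP 4.1 repeats it in general terms: "Additional analyses will be also carried out in the per-protocol and as-treated populations".

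SAP 3.3 builds crossover into the endpoint: "The primary endpoint is defined as LA patent or adjudicated cross-overs including failed cross-overs". SAP 4.2 then adds: "Crossover patients will be considered as a primary end-point event in all analyses". Its subsections define three sets: full analysis (as randomised), per-protocol and safety. None is called as-treated, and no other section defines one.

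Where the SAP does group by device received, it uses the implanted device. The safety population "is analysed according to the LAAC device actually implanted" (SAP 4.2.3). The footnote to Supplemental Table 1 in SAP 5.9 includes patients "randomized to Watchman / FLX, but were implanted a cross-over Amulet device instead".

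Protocol 8.4 says when a crossover is adjudicated as justified: the allocated device was positioned at least once, but sealing was inadequate or its stability was in doubt.

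**The concern.** An adjudicated crossover is information about the allocated device: it did not seal, or it was not judged stable. In the intention-to-treat and per-protocol analyses, which compare randomised arms, the event stays with that device, and the SAP 4.2 rule is right.

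An as-treated analysis ordinarily groups patients by what was implanted. A patient allocated to Watchman who ends with a well-sealing Amulet then leaves the Watchman group altogether and enters the Amulet group as a certain event. The analysis meant to show how the implanted device performed charges that device with the failure of the one it replaced. A shift from the intention-to-treat result could then be read as a difference in sealing when part of it is only a matter of which device the crossover is counted against.

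Two related points are also unspecified. Failed crossovers are events under SAP 3.3 but may leave no device implanted, so those patients have no as-implanted group. The device subgroup for the primary endpoint in SAP 6.2.4 does not say whether device means randomised, first attempted or implanted.

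**Working it through.** **Inputs from the documents.** Protocol 12.2 and SAP 2.3 give 200 patients, a composite rate of about 50% on Watchman/FLX and 30% on Amulet, and 5% alpha. Allocation is 1:1 (protocol 6.2), so 100 per arm.

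**The plan's own figure.** Two-sided 5% alpha (sidedness assumed) with pooled variance gives 82.8% power at 100 per arm, which agrees with the stated figure of more than 80%. The planned intention-to-treat result is 30/100 vs 50/100: 20.0 points, RR 0.60, chi-square p 0.004.

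**Assumptions.** The documents give no crossover rate. Let *a* be Watchman-to-Amulet and *b* Amulet-to-Watchman crossovers, all included in the 50 and 30 events and, unless stated, all implanted with the other device.

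**Formulas, grouped by device implanted.**

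- Under the rule (every crossover an event): Amulet (30 − b + a)/(100 − b + a); Watchman (50 − a + b)/(100 − a + b).
- Patency alone, no crossover patient patent: Amulet (30 − b)/(100 − b + a); Watchman (50 − a)/(100 − a + b).
- Patency alone, every crossover patient patent: same as under the rule.
- Largest effect of the rule when both directions share the same patency: a/(100 − b + a) − b/(100 − a + b). A positive value means the rule shrinks Amulet's advantage.

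**Results (Watchman minus Amulet, percentage points).**

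| a / b | Under the rule | Patency alone, none patent | Range of the rule's effect |
|---|---|---|---|
| 8 / 2 | 44/94 − 36/106 = 46.8 − 34.0 = 12.8 (RR 0.73, p 0.064) | 42/94 − 28/106 = 44.7 − 26.4 = 18.3 (RR 0.59, p 0.007) | 0 to 5.4 |
| 3 / 1 | 48/98 − 32/102 = 17.6 (p 0.011) | 47/98 − 29/102 = 19.5 (p 0.0045) | 0 to 1.9 |
| 5 / 5 | 50/100 − 30/100 = 20.0 | 45/100 − 25/100 = 20.0 | 0 |
| 2 / 8 | 56/106 − 24/94 = 27.3 | 48/106 − 22/94 = 21.9 | 0 to 5.4, reversed |

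For 8/2 the largest effect is 8/106 − 2/94 = 7.5 − 2.1 = 5.4 points.

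**Intermediate case.** Suppose crossover patients are patent at the rate of non-crossover patients on the device they received. At 8/2 those rates are 28/98 = 28.6% and 42/92 = 45.7%, a patency-alone difference of 17.1 points (p 0.012). The rule's effect is then 4.2 points (17.1 against 12.8, from unrounded values). At 5/5 the same assumption gives 21.1 against 20.0, an effect of 1.1.

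**Patency differing by direction.** At 8/2 the rule can change the difference by anything from −7.5 points (8/106) to +2.1 points (2/94).

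**Failed crossovers.** If 2 of the 8 end with no device and drop out, the rule gives 44/94 − 34/104 = 14.1 points, and patency alone with none patent gives 42/94 − 28/104 = 17.8. The effect is 6/104 − 2/94 = 3.6 points.

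**Separating two effects.** At 8/2 with none patent, the move from 20.0 to 18.3 comes from regrouping and dropping the crossover component, and the further move to 12.8 comes from the rule. Only the second is the defect.

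**The case against.** The strongest counter-argument is about reading. SAP 4.2 names the intention-to-treat and per-protocol analyses immediately before the crossover sentence, so its reach could be just those two, where it is correct. In addition, no section assigns the implanted-device grouping to the primary endpoint, and SAP 6.1 says outcomes are compared by randomised arm. This does not remove the problem. SAP 3.3 makes crossover part of the endpoint itself and protocol 12.4 plans that endpoint in the as-treated population, so crossovers are events there even on the narrow reading. Applying the randomised-arm comparison of SAP 6.1 would only repeat the intention-to-treat analysis.

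Second, as-treated patency is already a secondary outcome (SAP 6.1.2), so a reader has a measure of implanted-device sealing without crossovers. That is partly right and lowers the stakes. But that outcome is worded to cover arterial and/or venous phase, whereas the primary derivation is arterial only, and the planned as-treated composite stays unresolved.

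Third, the size is assumed and may be small: 5.4 points needs 10 crossovers in 200 patients, an 8:2 imbalance and no crossover patient patent. That stands. So does the point that no success criterion depends on this analysis. The SAP 6.2.4 wording alone would be only a missing detail.

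**Conclusion.** The concern holds. Read together, SAP 3.3, SAP 4.2 and protocol 12.4 produce an as-treated composite that, grouped by implanted device, assigns the allocated device's failure to its replacement. That grouping is not prescribed for this endpoint, but it is the ordinary meaning of as-treated and the only received-device grouping the SAP uses.

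The size depends on unknown crossover numbers and on patency among crossover patients. With both directions equally all patent or none patent, the rule's effect is 0 to 5.4 points at 8/2 and 0 to 1.9 at 3/1, with p below 0.05 either way at 3/1. It is nil when crossovers balance, and it favours Amulet when more patients cross from Amulet to Watchman. The main analysis, the per-protocol analysis and the power statement are untouched. This is a worthwhile correction to a supplementary analysis and no threat to the trial's main conclusion.

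**What to change.** In SAP 4.2:

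1. Add a definition: *As-treated population: patients with a LAAC device implanted, grouped by the device implanted. Patients with no device implanted are outside this population; failed crossovers among them remain primary events in the ITT analysis, and in the per-protocol analysis where they qualify.*
2. Replace the crossover sentence with: *Adjudicated crossovers, including failed crossovers, are primary events, counted against the randomised device, in the ITT and per-protocol analyses. In the as-treated population the outcome is 45-day arterial-phase CCTA patency alone, derived as in section 3.3, Table 1.* Naming Table 1 fixes the phase, since its reference value is "LA HU mean in arterial phase = artphase_mean1".
3. Record that this replaces the as-treated composite of protocol 12.4, under that section's clause: "Any deviation from the planned analyses will be reported in the final trial report".

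If the sponsor prefers to keep the composite, the crossover event should go to the first-attempted device (first_device, already used in SAP Table 2). This adds little: when every first attempt used the allocated device, it returns the intention-to-treat 20.0 points at the planning rates.

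State the grouping basis of the SAP 6.2.4 device subgroup at the same time. The primary endpoint definition and the CEC adjudication stay as they are.

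The cost is one definition, one reworded sentence and a short documented deviation, with the as-treated composite dropped or regrouped. Device implanted, first device, adjudicated crossover and arterial-phase HU are already recorded.
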